### **SYNOPSIS**

Title	Nottingham Gout Treatment Trial. Phase 2: Two Year Randomised Controlled Trial of a Nurse Led Package of Care		
Acronym	None		
Short title	Nottingham Gout Treatment Trial – Phase 2		
Chief Investigator	[name]		
Objectives	To determine in community-based patients with untreated or under treated gout the effectiveness and cost effectiveness of a nurse-led complex intervention that reflects recommended best practice (including urate lowering therapy (ULT) to reduce serum uric acid (SUA) levels to <360 µmol/l).		
Trial Configuration	Randomised, parallel group controlled trial comparing nurse led intervention with "standard" (GP led) care over a 2 year period  Multicentre study within the East Midlands and South Yorkshire (EMSY) Region.		
Setting	Primary Care, EMSY Region		
Sample size estimate	RCT: The sample size was estimated according to both primary and secondary outcomes. To achieve 90% power at 5% significant level (2-tailed), the sample size needed are: 70 patients for each group for reduction in SUA (primary outcome); 90 patients for each group for reduction in frequency of acute attacks in the final year, and 233 patients for each group for quality of life (QOL). Allowing a 10% drop-out rate over the 2 years, this requires a total of 512 patients (233 plus 36 dropouts in each arm) to provide adequate power for the primary outcome and for the 2 key secondary outcomes.		
Number of participants	Nurse intervention (RCT) – 256 Standard care (RCT) – 256		
Eligibility criteria	All – Adults aged 21 and over with GP diagnosis gout, confirmed following telephone interview to ensure that participants fulfil ACR criteria for gout.  Nurse intervention and standard care groups (RCT) – at least one acute attack of gout in the last year.		
Description of interventions	Nurse intervention arm – package of care based on best practice, including full information concerning nature and prognosis of gout, addressing illness perceptions of gout and possible barriers to care,		

Page **4** of **29** Final version 8 –18 May 2015

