### **STATISTICS**

### Methods

The trial statistician ([name]) will oversee the data management, evaluation and analyses. The database will be developed in collaboration with the CTU using access and analysed using SPSS. SUA will be analysed at baseline, 12 months and 24 months. Comparison will be undertaken between the nurse led intervention and control at each observational point. There will be no interim analyses for efficacy or safety. Intention to

Page **19** of **29** Final version 8 –18 May 2015

treat (ITT) analysis will be undertaken to compare treatment effects between groups. Multilevel models will be used for any missing outcome measures. Chi-square test will be used for dichotomous or categorical data and ANOVA test will be used for continuous variables. Adjustment will be made for baseline co-variables as appropriate. Cost per QALY will be estimated from the SF6D and the direct and indirect costs related to gout and its management.

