### Power calculations:

Information that includes SUA on community-derived patients with gout is sparse. However, detailed information on frequency of attacks, treatment, SUA and quality of life is available for 250 gout patients from 17 practices in Nottingham (5, 11). In this survey: 30% of patients were on ULT; the rate for acute attacks in the previous year was 32% for patients on ULT and 57% for patients on no ULT; mean SUA was 318  $\mu$ mol/L in those taking ULT compared to 434  $\mu$ mol/L in those not taking ULT; and 23% of those taking ULT had a SUA >360  $\mu$ mol/L, compared to 75% of those not on ULT. For quality of life (SF36) overall mean and SD for those on ULT was 16.41 (2.81) compared to 15.67 (3.05) for those not on ULT, giving a pooled SD of 3.09 and a mean difference of 0.7 between groups (the latter is used as a proxy of effect size d).

According to these results, we have estimated the following sample size requirements, to achieve 90% power at 0.05% significance level, for each outcome:

- reduction in frequency of acute attacks in final year a sample size of 90 is required for each arm
  - reduction in SUA below the therapeutic target a sample size of 70 patients is required for each arm
- quality of life a sample size of 233 is required for each arm (80% power at 0.05% significance level

Allowing a 10% drop-out rate over the 2 years, this requires a total of **512 patients** (233 plus 23 dropouts in each arm) to provide adequate power for the primary outcome and for 2 of the key secondary outcomes. There are no data on changes in GAQ in response to treatment, but being a disease-specific instrument, we assume that the GAQ will be more sensitive to change than the SF36 and that a total size of 796 will be adequately powered for this outcome.

The total number of GP practices in Nottinghamshire is 170 and the estimated number of registered patients with gout is 10,720 (i.e. an average of 65 patients per GP). A questionnaire will be sent to all patients (unless they have an exclusion criterion) to detect eligible patents. A random sample of those eligible will be selected using the simple random selection after the consent to the trial.

Page **20** of **29** Final version 8 –18 May 2015

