### **Secondary Efficacy Endpoints:**

Percentage in each group with reduced number of acute attacks in the second year of the study

Quality of life scores (SF36 and GAQ) at end point compared to baseline in each group and comparison of endpoint QOL scores between the two groups.

Reduction in size and number of tophi.

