# 2. Secondary outcomes

- Number of acute attacks in preceding year, year 1 and year 2 within each group and between groups
- Number of patients with tophi at baseline, 12 months and 24 months with each group and between groups
- Mean QoL scores (overall, different domain scores of SF36 and the Gout
   Asssessment Questionnaire (GAQ) including the Gout Impact Scale (GIS) of the GAQ.
   at 0, 12 and 24 months within each group and between groups
- Mean change of QoL scores from baseline to 12 months and 24 months within each group and between groups

**Covariates and baseline predictors:** age, gender, body mass index, disease duration, tophi, associated comorbidity etc.

Task allocation and timetable: The Nottingham CTU will undertake randomisation, development of the database for RCT and the web-based data entry platform. CTU will also conduct data monitoring and quality control for the RCT data. Academic Rheumatology will recruit patients, enter the data through a web-based data entry platform for the RCT data and develop an independent database for the observational group. Both datasets are not open for any interim analysis between baseline and 24 months to keep the randomisation. Analysis will start after 24 months when the data has been fully completed, quality checked over and closed. Analysis for clinical effectiveness (efficacy and side effects) will be completed in 3 months after the closing date of the data. Analysis for cost-effectiveness will be completed in 12 months, as it requires acquisition of additional data for cost. In brief:

- Recruitment 8 months
- RCT and observation 24 months
- Results for clinical effectiveness 3 months
- Results for cost-effectiveness 12 months

Economic Analyses Plan.

Two economic analyses are planned: the first being an economic analysis alongside the RCT and the second modelling the costs and benefits over a longer time horizon. The base case in both models would use an NHS perspective, with a societal perspective (that include indirect costs such as lost productivity) being undertaken in a sensitivity analysis.

Economic analysis alongside the RCT

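### No stated between-arm analysis of SF36, GAQ or mean SUA is specified to adjust for the outcome's own baseline value, although that value is collected in both arms

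*Supplement*

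**What the plan says.** - **Baseline data.** The regimen table in protocol version 8 has SF36, GAQ and SUA taken at baseline, 12 and 24 months in both arms.
- **Protocol comparison.** Secondary Efficacy Endpoints gives the between-arm quality-of-life result as a "comparison of endpoint QOL scores between the two groups"; comparison with baseline is described only within each group. Under Statistics, Methods, "ANOVA test will be used for continuous variables", with adjustment for baseline covariables where appropriate. The synopsis adds that this would be by multiple regression. Neither place says which covariables.
- **Analysis plan, items listed.** Secondary outcomes lists mean quality-of-life scores at each time and "Mean change of QoL scores from baseline to 12 months and 24 months", each within and between groups. Mean SUA is listed in the same two ways under the primary outcome.
- **Analysis plan, covariates.** The named ones are "age, gender, body mass index, disease duration, tophi, associated comorbidity etc". The baseline value of the outcome is not among them.
- **Analysis plan, model.** Principles of analysis calls the raw group differences descriptive. It gives the treatment comparison to a multilevel regression in which baseline, 12 and 24 months are all response rows, with group, time and baseline covariates as terms. It names no group-by-time term and no 24-month contrast.

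**The concern.** The baseline value of a score is usually one of the best predictors of its later value. Leaving it out of the between-arm comparison gives up precision that the trial has already paid for, and leaves a chance baseline difference uncorrected.

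This matters most for quality of life. It sets the trial's size (233 per arm, against 70 for the SUA target and 90 for attacks). The background section calls evidence of improved quality of life the one item missing for the planned policy submission. A phrase allowing adjustment where appropriate, and an open covariate list, also leave the choice to be made after the data are seen.

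**Working it through.** **Inputs.** From Power calculations in version 8: survey SF36 means of 16.41 (SD 2.81) with ULT and 15.67 (SD 3.05) without it, which the protocol summarises as "giving a pooled SD of 3.09 and a mean difference of 0.7 between groups". For the resulting sample size it states: "quality of life a sample size of 233 is required for each arm (80% power at 0.05% significance level". That section prints the level as 0.05%. The synopsis has "To achieve 90% power at 5% significant level (2-tailed), the sample size needed are", so two-sided 5% is used here. The correlation r between baseline and 24-month scores is not in the documents; 0.3 to 0.7 is an assumed range.

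**1. The plan's own figure.** n per arm = 2 (z₀.₉₇₅ + z₀.₈₀)² (SD/δ)² = 2 × (1.960 + 0.842)² × (3.09/0.7)² = 2 × 7.849 × 19.49 = 305.9, so 306. The stated 233 is not reproduced; at 80% power it corresponds to a standardised difference of 0.26, against 0.7/3.09 = 0.227. The synopsis also ties the same 233 to 90% power. These are separate sample-size inconsistencies. They are noted here only because they set the starting point.

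**2. End-score comparison at 233 per arm.** SE = 3.09 × √(2/233) = 0.286. 0.7/0.286 = 2.445. Power = Φ(2.445 − 1.960) = 68.6%.

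**3. Effect of using the baseline value.** With equal variance at both times, the variance of the treatment estimate is multiplied by 2(1 − r) for a change score and by 1 − r² for a baseline-adjusted comparison. Power is Φ(2.445/√factor − 1.960).

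| r (assumed) | End score | Change score | Baseline-adjusted | Gain over end score |
|---|---|---|---|---|
| 0.3 | 68.6% | 54.2% | 72.7% | 4.1 points |
| 0.5 | 68.6% | 68.6% | 80.6% | 12.0 points |
| 0.7 | 68.6% | 88.4% | 92.8% | 24.2 points |

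The adjusted analysis reaches 80% at 233 per arm when 1 − r² = 233/305.9 = 0.762, that is r of about 0.49.

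**4. Sensitivity to the starting point.** If the effect is instead the one that gives the end-score test its stated 80% (standardised difference 0.26), adjustment raises power to 83.6%, 89.9% and 97.5% at r = 0.3, 0.5 and 0.7: gains of about 4, 10 and 18 points.

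**5. Does the multilevel model already do this?** The wording allows three readings.

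- *Group main effect only.* The group coefficient averages the difference over three times, one of which is baseline, where the expected difference is zero. With equal weight to each time and the same effect at 12 and 24 months, it estimates (0 + 1 + 1)/3 = two thirds of the effect.
- *Group-by-time terms, arms free to differ at baseline.* With complete data and no other covariates, the 24-month contrast is the end-score difference and the interaction is the difference in mean change. Neither is adjusted for baseline.
- *Group-by-time terms with one common baseline mean.* This is close to baseline adjustment, but the plan names neither the terms nor the constraint.

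So putting baseline in as a response row does not by itself supply the adjustment.

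**The case against.** The best defence is that the plan does not rest on unadjusted tests. It labels raw differences descriptive and gives inference to a model that holds the baseline value as data and adjusts for baseline covariates. The covariate list is open-ended, the protocol permits adjustment, and version 8 names a single between-arm quality-of-life comparison, of endpoint scores. All of that stands. The baseline score is not excluded; it is simply never named. But permission to adjust does not prespecify an adjustment, and the model as described does not deliver it (step 5). A change score does use the baseline value, but with the slope fixed at 1: it is less efficient than adjustment for any r below 1, and less efficient than the end score when r is below 0.5.

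Three stronger readings are tempting, and the documents support none of them.

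- A reader might infer that the between-arm tests are simply raw. The descriptive label and the provision for adjustment say otherwise.
- A reader might infer that end scores and change scores could point in opposite directions. At r = 0.5, a baseline imbalance of one SE (0.29 points) moves the two estimates by +0.14 and −0.14, to about 0.84 and 0.56: the same direction. Reversing the expected change-score estimate would need an imbalance of 0.7/0.5 = 1.4 points, or 1.4/0.286 = 4.9 SE.
- A reader might infer a false-positive rate near 9% from having two tests. That figure requires that either raw result may be claimed as success. No passage says so, and the descriptive label points the other way.

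**Conclusion.** The point holds as a gap in prespecification with an efficiency cost. For SF36, GAQ and mean SUA, no stated between-arm analysis is specified to condition on the outcome's own baseline value, and the analysis plan does not name one 24-month contrast as the main result.

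For SF36 on the protocol's inputs, the gain available is about 4, 12 or 24 percentage points of power over 69% at r = 0.3, 0.5 or 0.7. This rests on the assumed correlation, equal variance at both times, a linear relation, 233 analysed per arm and a normal approximation. Only the gain belongs here; the shortfall from the stated 80% to 69% has another cause. No size is computed for GAQ or SUA. The primary endpoint, the percentage below the SUA target, is binary and is not covered by this arithmetic.

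**What to change.** For each continuous outcome (SF36, GAQ, SUA), name one main between-arm result: the 24-month difference adjusted for that outcome's own baseline value. Either of two models will do:

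- 12- and 24-month values as responses, baseline value as a covariate, with group-by-time terms; or
- all three times as responses, with group-by-time terms and a common baseline mean for the two arms.

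Do not simply add the baseline score to the covariate list while baseline remains a response row, because it would then be both response and covariate.

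Align Methods and Secondary Efficacy Endpoints in the protocol with this choice. State in the analysis plan that the between-group mean and mean-change items listed under its outcome measures fall under the descriptive analysis.

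The cost is wording in the two documents. The baseline values are already collected, and no participants, visits or measurements are added.

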### TRIAL / STUDY OBJECTIVES AND PURPOSE

### **PRIMARY OBJECTIVE:**

To determine in community-based patients with untreated or under treated gout the effectiveness and cost effectiveness of a nurse-led complex intervention compared to standard GP led care.

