### **DURATION OF THE TRIAL / STUDY AND PARTICIPANT INVOLVEMENT**

The total study duration will be 3 years, 8 months recruitment, 2 years participation and 4 months analysis and writing up. Each participant will be in the study for 2 years from the point of entry.

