### TRIAL / STUDY TREATMENT AND REGIMEN

The total study duration will be 3 years (8 month recruitment period, 2 years participation, 4 months analysis and writing up).

All appointments with our research nurses will be at the participants' local GP practice or in the participants' own home.

The study regimen is summarised in the table below (see also appendix1):

	RCT – nurse	RCT – control/
	intervention	standard care arm
Enquiry: age, sex, gout history, drug history, family history,	Х	X
comorbidities		
Individualised advice on management of acute attack	X	X
(selecting from ice packs, oral colchicine, oral NSAID plus		
PPI, corticosteroid).		
Provision of Arthritis UK patient booklet.	X	X
Tophi assessment (sites), if present	X	X
A clear verbal explanation of gout	X	
Individualised explanation of relevant risk factors	X	
Individualised advice on ways to reduce uric acid levels by	Х	
lifestyle modification, if appropriate		
Advice on ULT	X	
Height and weight (BMI)	X	X
Baseline/recruitment questionnaire (incl. SF36 & GAQ)	X	X
Serum uric acid, GFR and creatinine	X	X
Diary of acute attacks	X	X
Record of visits to GPs re gout management		X
SF36 'Quality of life' forms during acute attacks	Х	Х
12 month SUA	Х	X
12 month GFR & creatinine	Х	Х
12 month questionnaire (incl. SF36 & GAQ)	Х	X
12 month weight	Х	X

Page **15** of **29** Final version 8 –18 May 2015

24 month bloods	Х	X
24 month questionnaire (inl. SF36, GAQ, joint pain,	X	X
stiffness & function, gout attack triggers)		
24 month blood pressure	X	X
24 month weight	Х	Х

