# A community based randomised controlled trial comparing nurse-led intervention with standard care

# -Analysis plan

Synopsis of the design: A 2 year community based randomised controlled trial will be undertaken in Nottingham to investigate clinical effectiveness and cost-effectiveness of a nurse-led quality of care intervention versus standard of care control. A questionnaire survey will be undertaken in the GP practices in Nottinghamshire to obtain 724 patients with gout according to the American College of Rheumatology (ACR) criteria and at least one acute attack in the past year. They will be randomly allocated to the intervention and the control group using stratified (according to the participated GP practices), block (fixed block of 4 for random allocation to keep the balance between the groups) randomisation method. Participants will be examined at baseline, 12 months and 24 months for outcomes such as serum uric acid (SUA), number of acute attacks in the previous year and quality of life (QoL) (SF36).

Principles of analysis: Intention to treat (ITT) analysis will be conducted. Descriptive analysis on raw differences between groups at baseline, 12 months and 24 months will be undertaken. Multi-level regression model (MLM) will be used for the overall comparison of the treatment effect between groups with repeated measures and missing data. We shall include all data from 3 time points in the same model, with repeated measures as level 1 units and individuals as level 2 units. The treatment group and time points will be considered as covariates in the model together with covariates at baseline for the adjustment purpose. Continuous data (eg, SUA, QoL score, etc) will be analysed using MLM linear regression, whereas dichotomous and categorical data will be analysed using MLM logistic or multinomial models. Comparison will be made between the intervention and the control in the RCT, as well as between the control in the RCT and the observational group.

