This analysis would simply use the costs recorded in each arm of the trial and the utility of the patients, as estimated through the SF36 and SF6-D. Costs will relate to both the interventions and the consequences of the interventions, with both direct NHS costs and indirect costs recorded. Utility will be comprised of two parts, the underlying quality of life associated with patients with gout and decrements in utility associated with a flare. Utility will be combined with quantity of life to form quality-adjusted life years (QALYs).

The incremental costs associated with the nurse-led intervention will be divided by the incremental QALY gain to form a cost per QALY ratio that can be compared with current NICE thresholds. (http://www.nice.org.uk/media/B52/A7/TAMethodsGuideUpdatedJune2008.pdf)

Modelling the costs and benefits over a longer time horizon.

It may be the case that there are larger costs associated with the initial period of the nurse-led intervention and that these becoming markedly reduced over time. Contrastingly the benefits associated with a patient managing their disease more appropriately may remain constant. As such, limiting an economic analysis to the initial 2 year period may provide an over-estimate of the true cost per QALY ratio. In order that alternative cost per QALY ratios can be calculated a mathematical model would be constructed that can model a longer time horizon. This model would be consistent with NICE's reference case.

(http://www.nice.org.uk/media/B52/A7/TAMethodsGuideUpdatedJune2008.pdf)

If appropriate from the analysis of the RCT data, subgroup analyses would be undertaken in order to assess differential cost per QALYs across different patient types.

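### The within-trial cost-per-QALY analysis does not prespecify adjustment for baseline SF-6D, so the QALY difference is open to chance baseline imbalance and less precise than it need be

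*Supplement*

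**What the plan says.** The method is set out only in the analysis plan, under Economic analysis alongside the RCT: "This analysis would simply use the costs recorded in each arm of the trial and the utility of the patients", with utility obtained through the SF36 and SF-6D. Utility has two parts, "the underlying quality of life associated with patients with gout and decrements in utility associated with a flare". For the ratio, "The incremental costs associated with the nurse-led intervention will be divided by the incremental QALY gain". No regression, covariate or interpolation rule is given.

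Adjustment is mentioned in three other places:
- Analysis plan, Principles of analysis: baseline covariates enter a multilevel model with repeated measures at level 1 and individuals at level 2.
- Analysis plan, Covariates and baseline predictors: "age, gender, body mass index, disease duration, tophi, associated comorbidity etc". Baseline SF36 and SF-6D are not named, though the list is left open.
- Protocol version 8, synopsis (Statistical methods) and Statistics (Methods): baseline variables will be adjusted for where appropriate. The sentence on cost per QALY follows directly.

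The covariate is available. The version 8 regimen table marks "Baseline/recruitment questionnaire (incl. SF36 & GAQ" for both arms. On timing, "Participants will be examined at baseline, 12 months and 24 months for outcomes" that include SF36.

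**The concern.** A patient's utility at entry predicts utility at 12 and 24 months. If QALYs are formed as an area under the curve, entry utility is also part of the QALY itself. An arm that starts slightly higher by chance will then tend to accumulate more QALYs whatever care it receives. Without a baseline term, that head start is credited to the arm and enters the denominator of the ratio. Variation between patients that baseline utility could explain also stays in the standard error.

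Randomisation is stratified by GP practice only, which does nothing specific to balance utility. The primary objective covers the "effectiveness and cost effectiveness of a nurse-led complex intervention compared to standard GP led care", and the ratio is to be compared with NICE thresholds, so the precision of the QALY difference matters. Leaving adjustment open also allows the choice between adjusted and unadjusted results to be made after the ratio has been seen.

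**Working it through.** The documents state no standard error, power or sample size for the economic analysis, so there is no figure of the plan's own to reproduce. What follows sizes the effect of adding the covariate.

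**Inputs from the documents.** SF36 at 0, 12 and 24 months (analysis plan; version 8 regimen table). Two years per participant: "Each participant will be in the study for 2 years from the point of entry". 233 per arm after dropout (version 8, Power calculations).

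**Assumptions, not in the documents.** Trapezium QALY. The same SF-6D standard deviation *s* at each visit, taken as 0.12 (range 0.10 to 0.15). Between-visit correlation *r* of 0.4 to 0.7. The percentage cuts in standard error depend on neither *s* nor the sample size.

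**Equal correlation.** With Q = 0.5·u0 + u12 + 0.5·u24:
- Var(Q) = s²(1.5 + 2.5r)
- Cov(Q, u0) = s²(0.5 + 1.5r)
- R² = (0.5 + 1.5r)² / (1.5 + 2.5r)
- cut in standard error = 1 − √(1 − R²)

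r = 0.4: R² = 1.10²/2.50 = 0.484; cut = 1 − √0.516 = 28%.
r = 0.7: R² = 1.55²/3.25 = 0.739; cut = 1 − √0.261 = 49%.

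A simulation at r = 0.6, s = 0.12 and 233 per arm gave standard errors of 0.0190 unadjusted and 0.0115 adjusted. The formulas give 0.0193 and 0.0113.

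**Correlation decaying with time** (r over one year, r² over two). Var(Q) = s²(1.5 + 2r + 0.5r²) and Cov(Q, u0) = s²(0.5 + r + 0.5r²).

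r = 0.4: R² = 0.98²/2.38 = 0.404; cut = 23%.
r = 0.7: R² = 1.445²/3.145 = 0.664; cut = 42%.

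**Flare decrements** adding independent variance equal to a fraction *f* of Var(Q), with f assumed to be 0.25 to 0.50. R² becomes R²/(1 + f). Starting from equal correlation:

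r = 0.4, f = 0.50: R² = 0.484/1.50 = 0.323; cut = 18%.
r = 0.7, f = 0.25: R² = 0.739/1.25 = 0.591; cut = 36%.

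| Structure assumed | Cut in SE, r = 0.4 to 0.7 |
|---|---|
| Equal correlation, no flare variance | 28% to 49% |
| Decaying correlation, no flare variance | 23% to 42% |
| Equal correlation, flare variance 25% to 50% | 18% to 36% |

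**Carry-over of a chance imbalance.** A baseline difference d adds (0.5 + 1.5r)·d to the unadjusted QALY difference under equal correlation. One standard error of the baseline difference is 0.12·√(2/233) = 0.0111. The carry-over is 1.10 × 0.0111 = 0.012 QALY at r = 0.4 and 1.55 × 0.0111 = 0.017 at r = 0.7. With s from 0.10 to 0.15, the range is 0.010 to 0.022.

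**The case against.** The plan never calls the analysis raw or unadjusted. A reader might infer from its wording that adjustment has been deliberately ruled out, but the documents do not support that. The word about simply using trial data can equally be read as a contrast with the modelled longer horizon in the next subsection. The protocol's adjustment sentence stands next to the cost-per-QALY sentence and is not confined to clinical outcomes. This objection stands: the gap is in prespecification, and the plan has not declared a choice against adjustment. It does not close the gap, because the general sentence names neither QALYs nor baseline utility. The multilevel model with the stated covariates treats repeated measures, whereas a QALY is one total per patient.

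The plan also lists change from baseline for QoL scores. That appears among the clinical outcomes, and a change-based QALY is less efficient than regression on baseline. At r = 0.5 and s = 0.12 with 233 per arm, its standard error is 0.0147 against 0.0121.

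A reader might also infer that the unadjusted estimate is biased, or that imbalance could reverse the cost per QALY. Neither is shown. Randomisation keeps the unadjusted difference unbiased on average, and the documents give no expected cost or QALY difference against which to set 0.012 to 0.017 QALY.

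The trapezium rule, standard deviation and correlations are assumptions, and equal correlation without flare variance is the most favourable case shown. Finally, the synopsis lists cost effectiveness among the secondary outcomes, and serum uric acid is the only primary endpoint.

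**Conclusion.** The point holds as a gap in prespecification. The within-trial economic section specifies no adjustment for baseline SF-6D, and the general adjustment sentence permits it without requiring it for QALYs. The consequences are exposure to chance imbalance in this single trial and avoidable imprecision in the QALY difference.

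The size is conditional on the assumptions above. Over the structures tried, the standard error falls by somewhere between 18% and 49%, so calling the loss large is fair only towards the upper part of that range. The gain applies to the QALY difference alone. The cost per QALY also carries cost variance, which this covariate does not reduce, so the ratio's uncertainty will narrow by less. The change should be made, but the plan is not invalid without it.

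**What to change.** In the analysis plan, under Economic analysis alongside the RCT:
- state how QALYs are formed from the 0, 12 and 24 month SF-6D values and how flare decrements enter;
- prespecify a patient-level linear regression of two-year QALYs on arm and baseline SF-6D, and take the incremental QALY in the ratio from that model;
- estimate it jointly with the cost comparison, so that uncertainty in the ratio reflects both;
- carry the same adjusted estimate into the long-horizon model.

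An unadjusted result can be kept as a sensitivity analysis. The cost is a few sentences and one covariate derived from a questionnaire already completed in both arms. No new data, visits or participants are needed. The wording should be fixed before the data are opened for analysis.

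### The within-trial cost-effectiveness analysis is a bare cost-per-QALY ratio, with no sampling uncertainty and no handling of a zero or negative QALY difference

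*Supplement*

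**What the plan says.** The primary objective in protocol version 8 covers the "effectiveness and cost effectiveness of a nurse-led complex intervention compared to standard GP led care". The synopsis also lists cost effectiveness and cost utility among the secondary outcomes.

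The method is in the analysis plan under Economic Analyses Plan, in the part on the economic analysis alongside the RCT. It states: "This analysis would simply use the costs recorded in each arm of the trial and the utility of the patients". Then: "The incremental costs associated with the nurse-led intervention will be divided by the incremental QALY gain to form a cost per QALY ratio". The purpose is to "form a cost per QALY ratio that can be compared with current NICE thresholds".

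Three other statements bear on the point:

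- The one sensitivity analysis named for the economic work is a change of perspective: "with a societal perspective (that include indirect costs such as lost productivity) being undertaken in a sensitivity analysis".
- The commitment to the reference case, "This model would be consistent with NICE's reference case", stands in the part on the longer time horizon and refers to that model.
- The protocol's Statistics section, under Methods, adds only: "Cost per QALY will be estimated from the SF6D and the direct and indirect costs related to gout and its management".

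The protocol synopsis (statistical methods), the protocol's Methods and Cost Effectiveness and Utility sections, and the Economic Analyses Plan contain no confidence interval, bootstrap, net-benefit analysis, acceptability curve, adjustment for baseline utility, or rule for a dominated result.

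**The concern.** Incremental cost and incremental QALYs are both estimated with sampling error. A quotient of the two, reported without an interval, gives no indication of how far the answer could move in a repeat of the trial. When the QALY difference is near zero, the quotient is also unstable.

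The sign is a second problem. The plan speaks of a QALY gain and is silent on what happens if there is none. A negative ratio has two opposite meanings. An extra cost of £200 with a loss of 0.01 QALY gives 200/(-0.01) = -£20,000. A saving of £200 with a gain of 0.01 QALY gives (-200)/0.01 = -£20,000. Both lie below any positive threshold, yet in the first nurse care is dearer and worse, and in the second it is cheaper and better.

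At stake is the cost-effectiveness half of the primary objective: a single ratio under the threshold could be presented as support for nurse-led care when the data are equally compatible with no benefit.

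**Working it through.** The documents give no economic figure to reproduce: no cost SD, QALY SD, threshold value or economic power calculation. The check therefore asks how a bare comparison behaves when nurse care brings no QALY benefit.

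**Inputs**

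- From the protocol: 233 patients per arm (Power calculations, quality of life).
- From the analysis plan: nurse care may cost more, at least early on ("It may be the case that there are larger costs associated with the initial period of the nurse-led intervention").
- Assumed, not in the documents: true QALY difference 0; 2-year QALY SD 0.15-0.35; cost SD £300-800; true extra cost £100-400; threshold λ £20,000-30,000; the two estimated differences normal and independent.

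**Step 1: the 50% floor.** Let dC and dQ be the estimated cost and QALY differences. If dC = c > 0, then dC/dQ < λ occurs either when dQ < 0 (negative ratio) or when dQ > c/λ. With true QALY difference 0:

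P(ratio < λ) = 0.5 + P(dQ > c/λ) ≥ 0.5

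The 0.5 consists entirely of results in which nurse care is dearer and yields fewer QALYs. It needs no SD, and no value for λ beyond λ > 0, but it does need the cost difference to be positive in practically every sample.

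**Step 2: a worked example.** QALY SD 0.25, cost SD £300, extra cost £200, λ = £20,000.

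- √(2/233) = 0.0926
- SE(dQ) = 0.25 × 0.0926 = 0.0232
- SE(dC) = 300 × 0.0926 = £27.8
- Net benefit NB = λ·dQ − dC has mean −£200 and SE √((20,000 × 0.02316)² + 27.8²) = £464
- z = 200/464 = 0.431

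| Reading of the result | Probability of favouring nurse care |
|---|---|
| Ratio below λ, sign ignored | 0.5 + 0.333 = 83% |
| Point estimate of NB above 0 (dominated results read correctly) | 1 − Φ(0.431) = 33% |
| 95% CI of NB wholly above 0 | 1 − Φ(1.96 + 0.431) = 0.8% |

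**Step 3: the assumed range.**

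| Reading | Lowest | Highest |
|---|---|---|
| Ratio below λ, sign ignored | 58% | 96% |
| Point estimate of NB above 0 | 8% | 46% |
| 95% CI of NB wholly above 0 | below 0.1% | 2.0% |

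The 8% comes from QALY SD 0.15, cost SD £300, extra cost £400, λ = £20,000: SE(NB) = £279, z = 1.43. The 46% comes from QALY SD 0.35, cost SD £800, extra cost £100, λ = £30,000: SE(NB) = £976, z = 0.10.

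**Step 4: no effect on either cost or QALYs.** The sign-blind ratio lies below λ in 92-99% of trials and the point estimate of NB is above 0 in 50%. True net benefit is then exactly zero, so the 50% is not a rate of wrong decisions.

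**Step 5: where the floor fails.** If the sign of the cost difference is uncertain and costs and QALYs are strongly positively correlated, the sign-blind figure can drop below half. Cost SD £5,000, QALY SD 0.1, correlation 0.5, no cost difference and λ = £20,000 give 46%.

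**The case against.** A reader might infer that the plan declares nurse care cost-effective whenever the ratio is below the threshold, and so has a false-positive rate of at least 50%. The documents do not support that. The text says the ratio can be compared with thresholds; it names no figure, sets no success criterion and fixes no error rate. It also speaks of a QALY gain, so on its own words the ratio is formed where a gain exists, and a competent health economist would recognise a dominated result. The 50% floor and the 58-96% range therefore describe a sign-blind reading with clearly positive extra cost, not a rule in the plan. This objection stands.

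It can also be said that the ratio is not the only economic output, since a societal-perspective analysis and a longer-horizon model are planned, and that the within-trial text cites the same NICE methods guide as the model. The societal analysis does not address sampling error. The reference-case commitment is worded for the model alone. The guide's contents are not available here, and the within-trial citation follows the mention of thresholds, so it cannot be counted as a method for uncertainty.

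The multilevel models in the analysis plan might be thought to cover the gap. They are described for outcomes such as SUA and quality-of-life scores and are not linked to costs, QALYs or the ratio.

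Finally, every economic input except the 233 per arm is assumed. That is correct, and it limits the percentages. It does not affect the omission itself.

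**Conclusion.** The point holds as an omission in the stated method. The within-trial analysis yields one point-estimate ratio, without sampling uncertainty and without provision for a zero or negative QALY difference, although it serves part of the primary objective.

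If nurse care clearly costs more and adds no QALYs, a sign-blind comparison falls below any positive threshold at least half the time. With dominated results read correctly, a point-estimate comparison still favours nurse care in about 8-46% of trials. The second range depends on the assumed costs, SDs, thresholds and independence listed above; the first depends only on the cost difference being clearly positive. Both show how little a bare comparison can be relied on, and neither is an error rate that the plan sets.

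This is a worthwhile and cheap improvement. It does not touch the primary endpoint or the clinical comparison.

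**What to change.** Amend the economic section of the analysis plan as follows:

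- Make incremental net monetary benefit (threshold × QALY difference − cost difference) the within-trial estimate, at a threshold stated in advance.
- Adjust for baseline SF6D, which can be derived from the SF36 already collected at baseline.
- Give a 95% confidence interval, from a joint bootstrap of costs and QALYs or from a regression model.
- Show an acceptability curve over a range of thresholds.
- Report the ratio only when both differences are positive. Otherwise report the two differences, and label the result dominant or dominated where that applies.

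The cost is a few sentences of plan text and a little more analysis on data already being collected, with no change for participants. The downside is that the headline may have to be reported as uncertain instead of as one figure.
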